16.4 Vaccination-related Antibody Concentrations (Secondary Endpoint)

Analysis Set: Safety analysis set

Blood samples to assess levels of vaccination-related antibody concentrations will be collected pre dose, at Cycle 7, and at the end of treatment visit. Vaccination-related antibody concentration values will be provided in a listing by dose level.

17

References

1. Mosteller RD. Simplified calculation of body-surface area. N Engl J Med 1987;317:1098. PMID 3657876
3. Clopper CJ, Pearson ES (1934). The use of confidence or fiducial limits illustrated in the case of the binomial. Biometrika; 26, 404-413.

18 Appendices

Appendix I Description of the Case Review for Assessment of Immune-Related AEs and Definition of Infusion Related Reactions

In order to thoroughly and consistently analyze potential immune-mediated adverse events (AEs), a two-level approach is proposed including:

1. A MedDRA Preferred Term (PT) query is proposed for each event category (i.e., immune-mediated rash, colitis, pneumonitis, hepatitis, nephritis and renal dysfunction, endocrinopathies and other immune-mediated adverse reactions).
2. AEs identified by the MedDRA PT queries will then be medically reviewed using pre-defined case definitions for immune-mediated adverse reactions.

Level 1:

To identify potentially immune-mediated AEs, the MedDRA PT queries will be used to search for AEs of interest in the clinical database. The proposed event categories such as:

Immune-mediated rash, Immune-mediated colitis, Immune-mediated pneumonitis, Immune-mediated hepatitis, Immune-mediated nephritis and renal dysfunction, Immune-mediated endocrinopathies (Thyroid disorders: Hypothyroidism, Hyperthyroidism, and Thyroiditis), Immune-mediated endocrinopathies (Adrenal insufficiency, Immune-mediated endocrinopathies (Type 1 Diabetes Mellitus), Immune-mediated endocrinopathies (Pituitary dysfunction), Immune-mediated endocrinopathies (Hypogonadism), Other immune-mediated adverse events. Further details e.g. MeDDRA PT queries are regularly updated based on the current MeDRA version.

In order to standardize the MedDRA PT queries as much as possible, High Level Terms (HLT) and Standardized MedDRA Queries (SMQ) will be used whenever a choice, that is considered reflective of the events of interest, is available.

Level 2:

In a second level (medical review), the potential immune-mediated AEs identified from the search performed at Level 1, will be reviewed by qualified medical personnel to determine whether the AE meets the criteria (case definition) for an immune-mediated adverse reaction based on the following algorithm:

Table 10 Algorithm for immune-related adverse reactions

Criteria	Description
Onset	AE onset after 1st avelumab administration until up to 90 days after last dose
Duration	AE does not spontaneously resolve (i.e., without corticosteroids/ immunosuppressant treatment) within 7 days after onset
Immunosuppressive therapy	AE treated with corticosteroid or other immunosuppressant therapy. For endocrinopathies only: AE required hormone replacement* and /or (corticosteroid or other immunosuppressive therapy)
Etiology	No other clear etiology or Histopathology/biopsy consistent with immune-mediated event
All criteria listed in the left column need to be fulfilled for an event to meet the case definition of immune-mediated reaction.	
*Hormone replacement will be evaluated for specific endocrinopathy disorders only as follows: 
 • Thyroid disorders (HLT): Thyroid therapy (ATC codes (H03A, H03B)) • Diabetes mellitus (including hyperglycaemia): Insulin (ATC code A10A) 	

Infusion related reactions are identified based on a list of MedDRA PTs and criteria on the timely relationship according to Table 11.

Table 11 Criteria for infusion related reactions

Infusion related reactions	
Reactions - Considered when onset is on the day of avelumab infusion (during or after the infusion) or the day after the avelumab infusion (irrespective of resolution date):
 
 • Infusion related reaction • Drug hypersensitivity • Anaphylactic reaction • Hypersensitivity • Type 1 hypersensitivity 
Signs and Symptoms - occurring on the day of avelumab infusion (during or after the infusion) and resolved with end date within 2 days after onset
 
 • Pyrexia • Chills • Flushing • Hypotension • Dyspnoea • Wheezing • Back pain • Abdominal pain • Urticaria
----------------------------	--

ELECTRONIC SIGNATURES

Document: ctp-ms100070-0306-iap-v2

Signed By	Event Name	Meaning of Signature	Server Date (dd-MMM-yyyy HH:mm 'GMT'Z)
PPD	Task Completed (Approval eSign): Approved	Technical Approval	23-Jun-2021 15:22

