		Week 1 (Day 1)	Week 3 (Day 15)	Week 5 (Day 29)	Week 7 (Day 43)	Week 9 (Day 57)	Week 11 (Day 71)	Week 13 (Day 85)	> Week 13 (Day 85)	Within 7 Days of Decision to Discontinue	Visit 30 Days (± 5 days) After Last Tx	Phone Call 90 Days (± 5 days) After Last Tx	Every 12 Weeks (± 1 Week) After Last Tx
Concomitant medications and procedures f	X	Concomitant medications and procedures are collected through the Safety Follow-up Visit									X		
AE collection k		AEs are collected through the Safety Follow-up Visit Treatment-related non-serious AEs are collected until the 90-day Safety Follow-up Phone Call. b										X	
SAE collection k		All SAEs are documented through the 90-day Safety Follow-up Phone Call Ongoing SAEs at the 90-day Safety Follow-up Phone Call will be followed up b										X	
Samples and Laboratory Assessmentsl													
Hematology m	X	X	X	X	X	X	X	X	Q2 weeks	X	X		
Lymphocyte subset quantification n		X		X						X			
Coagulation (hemostaeology) o	X	X	X	X		X		X	Q4 weeks (odd- numbered cycles only)	X	X		
Full serum chemistry p	X	X								X	X		
Core serum chemistry p			X	X	X	X	X	X	Q2 weeks				
Urinalysis q	X	X		X		X		X	Q4 weeks	X	X		
Pregnancy test r	X	X		X		X		X	Q4 weeks	X	X		
T4 and TSH s	X	X		X				X	Q8 weeks	X			
Blood for cytokines t		X	X	X		X				X			
Blood for vaccination-related antibodies u		X						X		X			
HBV and HCV screening tests v	X												

		Treatment Period* (-3/+1 days) 1 Cycle = 14 Days								End Of Treatment/Follow-Up b			
Assessments	Screening (≤ 28 Days Prior to Enrollment)	Cycle 1	Cycle 2	Cycle 3	Cycle 4	Cycle 5	Cycle 6	Cycle 7	Until EOT	EOT/ Withdrawal Visit b	Safety Follow-up c		Survival Follow-up d
		Week 1 (Day 1)	Week 3 (Day 15)	Week 5 (Day 29)	Week 7 (Day 43)	Week 9 (Day 57)	Week 11 (Day 71)	Week 13 (Day 85)	> Week 13 (Day 85)	Within 7 Days of Decision to Discontinue	Visit 30 Days (± 5 days) After Last Tx	Phone Call 90 Days (± 5 days) After Last Tx	Every 12 Weeks (± 1 Week) After Last Tx
CCI CCI													
Baseline tumor evaluation/staging (CT/MRI/other established methods) x	X												

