Concomitant medications and treatments will be recorded from 28 days prior to the start of study treatment and up to 90 days after the last dose of study treatment (at Days 30 and 90 post-treatment  $\pm$  5 days). All concomitant medications, including supportive care drugs (eg, antiemetic treatment and prophylaxis), the drugs used to treat AEs or chronic diseases, and nondrug supportive interventions (eg, transfusions), should be recorded in the appropriate section of the eCRF, noting the name, dose, duration, and indication of each drug. Nondrug interventions and any changes to a concomitant medication or other intervention should also be recorded in the eCRF.

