
Grade 3 or Grade 4 endocrinopathies (hypothyroidism, hyperthyroidism, adrenal insufficiency, type I diabetes mellitus)
	
Withhold avelumab therapy Consider hospitalization Endocrinology consult
 
Start thyroid hormone replacement therapy (for hypothyroidism), anti-thyroid treatment (for hyperthyroidism), corticosteroids (for adrenal insufficiency), or insulin (for type I diabetes mellitus) as appropriate.
 
Rule-out secondary endocrinopathies (ie, hypopituitarism / hypophysitis)
	
Resume avelumab once symptoms and/or laboratory tests improve (with or without hormone replacement/suppression).
 
Continue hormone replacement/suppression and monitoring of endocrine function as appropriate

Hypopituitarism/Hypophysitis (secondary endocrinopathies)
	
If secondary thyroid and/or adrenal insufficiency is confirmed (ie, subnormal serum T4 with inappropriately low TSH and/or low serum cortisol with inappropriately low ACTH) :
 
 
Refer to endocrinologist for dynamic testing as indicated and measurement of other hormones (FSH, LH, GH/IGF-1, prolactin, testosterone in men, estrogens in women)
 
Start hormone replacement/suppressive therapy as appropriate
 
Perform pituitary MRI and visual field examination as indicated
 
 
If hypophysitis confirmed:
 
 
Continue avelumab if mild or moderate symptoms with normal MRI. Repeat the MRI in 1 month
 
	
Resume avelumab once symptoms and hormone tests improve (with or without hormone replacement).
 
In addition, for hypophysitis with abnormal MRI, resume avelumab only once shrinkage of the pituitary gland on MRI scan is documented.
 
Continue hormone replacement/suppression therapy as appropriate.

	
 
Withhold avelumab if severe symptoms or life-threatening symptoms of hypophysitis and/or abnormal MRI. Consider hospitalization. Initiate high-dose corticosteroids (1 to 2 mg/kg/day methylprednisolone iv or equivalent) followed by corticosteroids taper during at least 1 month.
 
	
Other irAEs (not described above)		
Grade of other irAEs (NCI-CTCAE v4.03)	Grade of other irAEs (NCI-CTCAE v4.03)	Grade of other irAEs (NCI-CTCAE v4.03)

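### The SAP searches for immune-mediated hypogonadism and pituitary dysfunction, but the Table 10 footnote gives neither a hormone-replacement route, so cases managed only with non-corticosteroid hormones drop out of the final irAE analysis

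*SAP*

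**What the plan says.** **Search (SAP Appendix I, Level 1).** The endocrine categories are thyroid disorders, adrenal insufficiency, type 1 diabetes and two more: "Immune-mediated endocrinopathies (Pituitary dysfunction), Immune-mediated endocrinopathies (Hypogonadism").

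**Case definition (SAP Appendix I, Level 2, Table 10).** Medical reviewers decide whether each event found meets criteria on onset, duration, immunosuppressive therapy and etiology. The combination rule is strict: "All criteria listed in the left column need to be fulfilled for an event to meet the case definition of immune-mediated reaction". For endocrinopathies the treatment criterion reads "AE required hormone replacement* and /or (corticosteroid or other immunosuppressive therapy"). The asterisk leads to a footnote: "Hormone replacement will be evaluated for specific endocrinopathy disorders only as follows". Its first entry is "Thyroid disorders (HLT): Thyroid therapy (ATC codes (H03A, H03B")); its second and last is diabetes with insulin (A10A).

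**Use.** SAP Section 15.2 applies this definition to the final analysis. SMC meetings use a preferred-term list of potential irAEs instead. Sections 15.2.1 and 15.3.3 tabulate treatment-emergent irAEs, which are adverse events of special interest and part of a secondary endpoint.

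**Protocol on treatment.** In the hypopituitarism/hypophysitis row of Table 5, once secondary thyroid and/or adrenal insufficiency is confirmed, the instruction is "Start hormone replacement/suppressive therapy as appropriate". High-dose corticosteroids are named there only for severe or life-threatening hypophysitis symptoms and/or an abnormal MRI.

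**Protocol on recording.** Table 1 states "Concomitant medications and procedures are collected through the Safety Follow-up Visit", and footnote j agrees. Section 6.5.2 has recording continue "up to 90 days after the last dose of study treatment (at Days 30 and 90 post-treatment").

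**The concern.** The two levels of the algorithm do not match. Level 1 treats hypogonadism and pituitary dysfunction as immune-mediated categories worth finding. Level 2 makes treatment compulsory, accepts hormone replacement in principle, and then names no qualifying hormone for these two groups. The result follows from the stated rule and does not depend on a reviewer's judgement: Appendix I asks only whether the criteria are met and gives no override.

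At stake is the completeness of the irAE tables and listing in a trial where every subject is under 18. The protocol already measures LH, FSH, estradiol, testosterone and IGF-1 at Baseline and annually, for effects on growing bone (Table 1, footnote i). A final report could therefore show no endocrine irAE of these kinds although the search had found a candidate and the child had received replacement.

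**Working it through.** The plan states no figure to reproduce. The check is a logic trace of Table 10.

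**Rule**

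- irAE = Onset AND Duration AND Treatment AND Etiology.
- For endocrinopathies, Treatment = (corticosteroid or other immunosuppressant) OR (thyroid disorder AND H03A/H03B) OR (diabetes AND A10A).

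**Trace**, taking Onset, Duration and Etiology as met:

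| Event group (Level 1) | Treatment given | Treatment criterion | irAE? |
|---|---|---|---|
| Thyroid disorder | H03A or H03B | Met, footnote | Yes |
| Type 1 diabetes | Insulin, A10A | Met, footnote | Yes |
| Adrenal insufficiency | Corticosteroid | Met, corticosteroid route | Yes |
| Pituitary dysfunction | Any corticosteroid, including physiological replacement | Met, corticosteroid route | Yes |
| Pituitary dysfunction | Non-corticosteroid hormones only | Not met | No |
| Hypogonadism | Sex hormone only | Not met | No |

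Of the five endocrine groups searched, the footnote covers two and the corticosteroid route covers adrenal insufficiency. That leaves 5 − 2 − 1 = 2 groups without a hormone route of their own. For pituitary dysfunction the gap is partial, as the fourth row shows.

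**Direction.** The omission can turn a yes into a no and never the reverse, so the irAE count can only fall.

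**Scale of one event.** Protocol Section 5.1.1 plans 12 to 36 Phase I subjects. One reclassified child is 1/12 = 8.3% at the lower end and 1/36 = 2.8% at the upper end. This is the weight of a single case, not an estimate of how many occur.

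**Medication recording.** Three windows bear on the treatment criterion:

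- Onset accepted by Table 10: to 90 days after last dose.
- Events counted in the irAE tables: onset within the on-treatment period, which ends 30 days after last dose or the day before new anti-cancer drug therapy, whichever is earlier (SAP Section 9).
- Concomitant medication: to the 30-day visit (±5 days, so Day 25 to Day 35) under Table 1 and footnote j; to 90 days under Section 6.5.2.

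Onsets after Day 30 are outside the tables whatever medication is collected. The case that matters there is an event with onset inside the on-treatment period whose first treatment starts after the 30-day visit. A site following Table 1 would have no ATC-coded record of that treatment.

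**The case against.** The best opposing case is that the effect is narrow and concerns a label. Much of this stands.

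- **The events are not lost.** On-treatment events remain in the TEAE tables and, where applicable, the related, serious and Grade ≥ 3 counts. The hormone assays are listed under SAP Section 15.4.2, and the SMC search has no treatment criterion. No DLT decision or primary endpoint is affected.
- **Corticosteroid can itself be replacement.** A reader might infer that pituitary dysfunction managed with hormones can never qualify. That goes too far: secondary adrenal insufficiency replaced with a corticosteroid passes.
- **Protocol Table 5 does not describe isolated hypogonadism.** Its hormone work-up is conditional on confirmed secondary thyroid or adrenal insufficiency, and no row covers sex-hormone deficiency alone. The catch-all row for other irAEs names prednisone from Grade 2, so a case handled under that row would pass by the corticosteroid route. Table 5 shows that hormone replacement is foreseen for pituitary disease; it does not show how often steroid-free cases would arise.
- **Central hypothyroidism.** It is tempting to say that it fails too. That depends on whether the event is coded as a thyroid disorder or under the pituitary query, and the SAP does not reproduce the queries.
- **The definition may be a programme standard.** SAP Section 6 refers to avelumab standards for analyses, so a study-specific change costs some comparability.

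None of this supplies the missing route. With all criteria compulsory and no override, the last two rows of the trace still fail.

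**Conclusion.** The concern holds for two situations: hypogonadism treated only with sex hormones, and pituitary dysfunction treated only with non-corticosteroid hormones, unless the event is coded as a thyroid disorder and given thyroid therapy. Neither can be classified as an irAE in the final analysis, although Appendix I searches for both. The error runs one way, towards under-counting. Its size cannot be computed, because the documents give no rate for these events and no expected split of treatments.

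This rests on reading the footnote as exhaustive, which its wording supports, and on reviewers applying Table 10 as written.

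Two further inferences are not supported. A reader might take the 60-day difference between the two medication windows (90 − 30) as a measure of bias in the irAE tables. It is not, because those tables stop at 30 days after last dose. A reader might also attach confidence intervals to an irAE proportion to show what would be misreported, but SAP Section 15.3.3 plans only numbers and percentages. The medication conflict is a real inconsistency within the protocol, with a small and separate bearing on this endpoint. Even there, Protocol Section 7.4.1.2 asks each AE report to include any treatment given, so late treatment may be visible to a reviewer without a coded medication record.

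**What to change.** 1. **SAP Appendix I, Table 10 footnote.** Before database lock, add entries so that hormone replacement counts for hypogonadism (sex hormones) and for pituitary dysfunction (replacement of any deficient pituitary axis), each with the matching ATC classes. This alters classification only and leaves patient management untouched.
2. **Reporting.** Show the irAE count under the extended definition and, beside it, under the present one. This keeps comparability with other avelumab studies if Table 10 is a programme standard.
3. **Protocol Table 1, footnote j and Section 6.5.2.** Reconcile the 30-day and 90-day recording periods, and state in the SAP which medication records the Table 10 review may use for on-treatment events first treated after the 30-day visit.

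The cost is two footnote lines, a few more codes in the review listing and one extra count. The irAE count may rise slightly, and the definition departs a little from the programme standard. If 90 days is the agreed recording period, the 90-day call needs a medication question, which Section 6.5.2 already implies.
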